- e. In participants with DCM related to pathogenic or likely pathogenic variants of TTN, DCM must not be secondary to significant exposure to cardiotoxic chemotherapy agents, as determined by the Investigator.
- f. In participants with DCM related to pathogenic or likely pathogenic variants of TTN, DCM must not be due to a history of significant alcohol abuse, as determined by the Investigator.
- g. Documented LVEF 15 to 45% (on 2 occasions), including at least once during Screening and confirmed by the Echo Core Laboratory.
 - If a participant's most recent prior TTE (within past 12 months) documents a LVEF ≤ 45%, then only a single Screening visit confirming LVEF ≤ 45% by the Echo Core Laboratory is required.
 - If no prior documented $LVEF \le 45\%$ by TTE within the past 12 months is available, then 2 Screening TTEs are needed at least one week (7 days) apart.
 - In addition, the absolute difference between the 2 LVEF values qualifying the participant should be < 12%.
- h. Participant receives chronic medication for the treatment of heart failure reflecting current guidelines, including at least one of the following, unless not tolerated or contraindicated: β -blocker, angiotensin converting enzyme inhibitor, angiotensin receptor blocker, or angiotensin receptor neprilysin inhibitor. Such treatments should have been given at stable doses for ≥ 2 weeks with no plan to modify during the study.
- I4. Sinus rhythm or stable atrial or ventricular pacing or persistent atrial fibrillation that is adequately rate-controlled to allow PD assessments by TTE.

NOTE: Participants with implanted cardioverter defibrillator, pacing, or cardiac resynchronization therapy are eligible if provided device programming is unchanged starting 2 months prior to and throughout the dosing period.

- 15. If multiple members of a family meet eligibility criteria, a maximum of 3 eligible participants per family may enroll in the study.
- I6. Female participants of childbearing potential (Appendix 6) must not be pregnant or lactating and, if sexually active, must use one of the following highly effective birth control methods from the Screening visit through 3 months after the last dose of study drug
- combined (estrogen- and progestogen-containing) hormonal contraception associated with inhibition of ovulation or progestogen-only hormonal contraception associated with inhibition of ovulation by oral, implantable, or injectable route of administration
- intrauterine device (IUD)

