- I2. Participant receiving chronic medication for the treatment of heart failure reflecting current guidelines, including at least one of the following, unless not tolerated or contraindicated: β -blocker, angiotensin converting enzyme inhibitor, angiotensin receptor blocker, or angiotensin receptor neprilysin inhibitor. Such treatments should have been given at stable doses for ≥ 2 weeks prior to the start of Part B.
- 13. Sinus rhythm or stable atrial or ventricular pacing or persistent atrial fibrillation that is adequately rate-controlled to allow PD assessments by TTE.

NOTE: Participants with implanted cardioverter defibrillator, pacing, or cardiac resynchronization therapy are eligible if provided device programming is unchanged starting 2 months prior to Part B.

- I4. Female participants of childbearing potential (Appendix 6) must not be pregnant or lactating and, if sexually active, must use one of the following highly effective birth control methods after participants signed Part B informed consent through 3 months after the last dose of study drug
- combined (estrogen- and progestogen-containing) hormonal contraception associated with inhibition of ovulation or progestogen-only hormonal contraception associated with inhibition of ovulation by oral, implantable, or injectable route of administration
- intrauterine device (IUD)
- intrauterine hormone-releasing system (IUS)
- Female participant is surgically sterile. Surgical sterilization includes documented hysterectomy, bilateral oophorectomy, bilateral salpingectomy, and/or bilateral tubal occlusion or ligation before and/or at the signing of the Part B informed consent execution.
- Female participant postmenopausal for 1 year. Female subjects are considered postmenopausal if they have had amenorrhea for at least 1 year or more following cessation of all exogenous hormonal treatments, and follicle-stimulating hormone (FSH) levels are in the postmenopausal range.
- Male partners must also use a contraceptive (eg, barrier, condom, or vasectomy).
 - I5. Male participants must use barrier method of contraception (whether or not the participant had vasectomy).

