Note 1: If no Rescreening Visit is required, the following criteria must be evaluated by or at Part B Baseline Visit prior to dosing.

- E1. Recent (< 90 days) acute coronary syndrome or angina pectoris.
- E2. Coronary revascularization (percutaneous coronary intervention or coronary artery bypass graft) within prior 90 days.
- E3. Recent (< 90 days) hospitalization for heart failure, use of intravenous diuretic or chronic intravenous inotropic therapy or other cardiovascular event (eg, cerebrovascular accident).
- E4. Active infection, indicated clinically as determined by the Investigator. In the case of SARS-CoV-2 (COVID-19) infection within 4 weeks prior to Part B Baseline Visit or Rescreening (if required), symptoms must have completely resolved and based on Investigator assessment in consultation with the Clinical Trial Physician, there are no sequelae that would place the participant at a higher risk of receiving investigational treatment. The methods to assess SARS-CoV-2 (COVID-19) infection include PCR, antigen test and serology tests. Each study site should follow requirements per local institutional or regulatory guidance if any.
- E5. For participants who need Rescreening, severe renal insufficiency (defined as current eGFR < 30 mL/min/1.73 m2 by simplified sMDRD).

- E6. For participants who need Rescreening, any persistent (2 or more) out-of-range safety laboratory parameters (chemistry, hematology), considered by the Investigator and the Medical Monitor to be clinically significant.
- E7. WOCBP participants with a positive pregnancy test.
- E8. History or evidence of any other clinically significant disorder, condition, or disease (including substance abuse) that, in the opinion of the Investigator or the Sponsor Physician, would pose a risk to participant safety or interfere with the study evaluation, procedures, completion, or lead to premature withdrawal from the study.
- E9. Is employed by or is a first-degree relative of someone employed by the Sponsor, the Investigator, or his/her staff or family.
- E10. Currently placed in hospital or facility due to legal or administrative order.
- E11. Not have an implantable cardioverter defibrillator despite meeting the conditions of class I recommendation defined in 2022 AHA/ACC HF guidelines (7.4.1) or the 2021 ESC HF guideline, depending on the region where participants reside.

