Visit Number	V0A	V1.1A	V1.2A	V2A	TH1A	V3A	TH2A	V4A/ EOT (Part A)	ТНЗА	V5A/ EOS (Part A) ^a	ЕТА
Telehealth Visit					Xs		Xs		X		
Tx Period 1 Study Drug Administration ^p				•							
Tx Period 2 Study Drug Administration ^p							•				
Study Drug Compliance Check ^q					Х	Х	Х	Х			

Table 3:Schedule of Assessments, Part A

AE = adverse event; CV = cardiovascular; DCM = dilated cardiomyopathy; ECG = electrocardiogram; EOS = end of study; ET = early termination Part A FSH = follicle-stimulating hormone; hsTnI = high sensitivity troponin I; hsTnT = high sensitivity troponin T; IMP = investigational medicinal product; KCCQ-23 = Kansas City Cardiomyopathy Questionnaire (23-item version); MYH7 = Myosin Heavy Chain 7; NT-proBNP = N-terminal pro b-type natriuretic peptide; NYHA = New York Heart Association; PK = pharmacokinetic; SAE = serious adverse event; TH = telehealth; TTE = transthoracic echocardiography; TTN = titin; TX = treatment; V = visit.

- ^a If a Rescreening visit is not required prior to Part B start, then Visit 1B can be performed on the same day as Visit 5A and any assessments in Visit 5A that are also required in Visit 1B need to only be performed once.
- ^b Where allowed by local regulations, participants may consent to share results of previous genetic testing. These results will be shared with the Sponsor for assessing potential eligibility prior to Visit 1A (Screening).
- ^c Pregnancy tests, urine or serum, is based on the policy of the local institution or regulating Health Authority (eg, requirement for serum-based testing in the United Kingdom) should be performed on all females of child-bearing potential at Screening, Day 1, and Follow-up.
- ^d At Screening, a complete physical examination will be conducted including a neurological examination (gross motor and deep tendon reflexes), height and weight, and assessment of the following: general appearance, skin, head and neck, mouth, lymph nodes, thyroid, abdomen, musculoskeletal, cardiovascular, neurological, and respiratory systems. All other timepoints can be abbreviated physical examination (pulmonary, cardiac, abdominal, and other systems related to any symptoms).

- ^e Participant should be at rest for at least 10 minutes prior to performance of any TTE. At least one full TTE must be performed at Screening. Eligibility to be determined by criteria in Section 7.1.
- ^f TTE at Visit 3A will be reviewed locally in real time to determine dosing of study drug for Treatment Period 2.

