- ^u Triplicate 12-lead ECG obtained at Visit 3A will be reviewed by the Investigator to confirm lack of QTcF prolongation in order to continue with study drug treatment (Section 6.2) before being sent to the ECG core laboratory.
- ^v Changes in baseline conditions from once the ICF is signed will be recorded as an AE. All changes, unless otherwise specified, that occur after the administration of study drug will be considered treatment emergent AEs.
- ^w FSH level assessment done at Screening is only for women of non-childbearing potential.
- ^x Should be done before any other assessments.
- ^y If rescreening is conducted, repeat of genetic testing at Screening is not necessary. Up to 1 rescreen per participant is permitted.

Table 4:Schedule of Assessments, Part B (Active Cohort)

	End of Part A					Part B,	Year 1					
Visit Day	14 days + 7d after V4A	Day -28 to -1 (Rescreening, if needed)	Day 1 (Baseline)	Week 2	Week 6	Week 12	Week 18	Week 24	Week 30	Week 36	Week 42	Week 48
Visit Number	V5A ^a	V0B ¹	V1B ^a	V2B	V3B	V4B	V5B	V6B	TH1B	V7B	TH2B	V8B
Visit Windows		-28 days		±2 days	±7 days	±7 days	±7 days	±7 days	±7 days	±7 days	±7 days	±7 days
Telehealth Visit									X		X	
Informed Consent		Х	X (if needed)									
Medical History		Х	X (if needed)									
Vital Signs		Х	Х	Х	Х	Х	Х	Х	Xi	Х	Xi	Х
Weight		Х	Х	Х	Х	Х		Х				Х
Complete Physical Exam		Х										
Symptom-directed Physical Exam			Х	Х	Х	Х	Х	Х		Х		Х
TTE			X ^d	X ^{c,e}	X ^{c,e}	X°		X°				X°
12-lead ECG	Х	Х	Х	Х	Х	Х	Х	Х	Xi	Х	Xi	Х
Cardiac Rhythm Monitoring ^f			Х					Х				Х
Activity Monitor ^g			Х					Х				Х
CMR ^h			X ^d									Х
6MWD (in clinic)			X ^d					Х				Х
NYHA Functional Classification	Х		Х		Х	Х	Х	Х		Х		Х
KCCQ-23	Х		Х		Х	Х	Х	Х	Х	Х	Х	Х
hsTnT/TnI/hs-TnI (Central) ^b	Х		Х	Xj	Xj	Xj	Xj	Xj	Xj	Х	Xj	Х

Table 4:Schedule of Assessments, Part B (A	Active Cohort)
--	----------------

	End of Part A					Part B,	Year 1					
Visit Day	14 days + 7d after V4A	Day -28 to -1 (Rescreening, if needed)	Day 1 (Baseline)	Week 2	Week 6	Week 12	Week 18	Week 24	Week 30	Week 36	Week 42	Week 48
Visit Number	V5A ^a	V0B ¹	V1B ^a	V2B	V3B	V4B	V5B	V6B	TH1B	V7B	TH2B	V8B
Visit Windows		-28 days		±2 days	±7 days	±7 days	±7 days	±7 days	±7 days	±7 days	±7 days	±7 days
Telehealth Visit									Х		X	
NT-proBNP (Central)	Х		Х	Х	Х	Х	Х	Х	Xj	Х	Xj	Х
Chemistry, Hematology (Central)	Х	X°	Х	Х	Х	Х	Х	Х		Х		X
Pregnancy Test ^k	Х	Х						Х				Х
Danicamtiv Plasma PK Sample			X (pre- dose_	Xc	Xc	Xc	Х	Xc		Х		Xc

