^a If a Rescreening visit is not required prior to Part B start, then Visit 1B can be performed on the same day as Visit 5A and any assessments in Visit 5A that are also required in Visit 1B need only be performed once. If Visits 5A and 1B are not performed on the same day, Part B Medical History assessment to be done on study participants who require Rescreening Visit for Part B (V0B) or sign the Part B ICF at V1B and are less than or equal to 56 days from completion of Part A.

^b If TnI (standard) is elevated, telehealth visits should be converted to clinic visits; see footnote j.

^c Perform a TTE and dani plasma PK sample collection at approximately 7 hours (± 1 hour) after the morning dose on every visit after Day 1.

- ^d Can be done within 7 days of the initial starting dose in Part B
- e

g

^f Cardiac rhythm monitoring patch will be placed at Visit 1B, 6B, 8B, 10B, and EOT. The duration of initial monitoring is for a maximum of 14 days. If the patch should become detached prior to 5 days, a new patch should be placed as soon as possible. Once patch detaches after at least 5 days, participants will be instructed to mail the patch back to the site.

- ^{h.} CMR to be scheduled prior to dosing (prior to Visit 5A/Visit 1B if combining visits) and then within 4 weeks of each 1 year anniversary on study. CMR will be obtained only in suitable participants.
- ¹ A 12-lead ECG and vital signs will be performed if TnI (standard) is elevated by more than 0.05ng/mL (see footnote h).

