- ^j If TnI (standard) level is below ULN at Baseline and subsequently increases to more than 0.05 ng/mL, or if TnI level is above ULN at Baseline and then subsequently increases by more than 0.05 ng/mL above the participant's Baseline value (obtained at Visit 1B in Part B) until Visit 6B (Week 24), the totality of the clinical data will be reviewed by a panel of experts periodically to determine if any signs of ischemia are seen. During this time, the participant will continue danicamtiv at the same dose; subsequent telehealth visits will become in-person clinic visits with 12-lead ECGs, vital signs, and collection of TnI, hsTnI, TnT, and NT-proBNP until troponin levels are stable or declining. If TnI (standard) level exceeds 0.1 ng/mL at any time, the participant will be requested to return for repeat evaluation as soon as possible. If this level of TnI (standard) is confirmed, treatment with danicamtiv will be temporarily discontinued and an ad hoc expert review will be triggered. If TnI (standard and high sensitivity) and hsTnT are collected at visits TH1B and TH2B, then NT-proBNP should also be collected in the same blood draws.
- ^k Pregnancy tests, urine or blood, is based on the policy of the local institution or regulating Health Authority (eg, requirement for serum-based testing in the United Kingdom).
- ¹ Rescreening visit to be performed only if timeframe between completion of Part A to start of Part B is greater than 56 days.
- ^m Changes in baseline conditions from once the ICF is signed will be recorded as an AE. All changes, unless otherwise specified, that occur after the administration of study drug will be considered treatment-emergent AEs.
- ⁿ Study drug compliance check will entail table count at all Part B visits including telehealth visits. Acceptable methods of contact include, but are not limited to, telephone, two-way text messaging and email.
- ^o Screening laboratory tests will include TSH and Fe/TIBC/ferritin to exclude uncontrolled thyroid functions and Fe overload.

	Part A							
Visit Day	14 days + 7d after V4A	Day -28 to -1 (Rescreening, if needed)	Day 1 (Baseline)	Week 12	Week 24	Week 48	Week 96	
Visit Number	V5A	voo ^b	V10 ^c	V2O	V30	V40	V50	
Visit Windows		-28 days		± 14 days	± 14 days	± 14 days	± 14 days	
Telehealth Visit								
Informed Consent		Х	X (if needed)					
Medical History		Х	X (if needed)					
Vital Signs		Х	Х	Х	X	Х	Х	
Weight		Х	Х		X	Х	Х	
Symptom-directed Physical Exam			Х		X	Х	Х	
TTE			Xa	Х	X	Х	Х	

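### Table 4 schedules no pregnancy test at Visit 1B, so some women can start Part B dosing on a result up to 56 days old (42 if counted from Visit 4A)

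*Combined protocol and SAP*

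**What the plan says.** Section 7.1, Part B criterion I4, requires that women of childbearing potential "must not be pregnant or lactating". Section 7.2, Part B criterion E7, excludes "WOCBP participants with a positive pregnancy test". For anyone not rescreened, Note 1 in Section 7.2 says "the following criteria must be evaluated by or at Part B Baseline Visit prior to dosing". None of these sets a maximum age for the result.

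The schedule is in Appendix 1. In Year 1 of Table 4, the row "Pregnancy Test" is marked at Visits 5A, 0B, 6B (Week 24) and 8B (Week 48). It is blank at Visit 1B. Two footnotes decide who reaches Visit 1B without a newer test:

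- Footnote l, on rescreening (Visit 0B): "Rescreening visit to be performed only if timeframe between completion of Part A to start of Part B is greater than 56 days".
- Footnote a, when rescreening is not needed: "then Visit 1B can be performed on the same day as Visit 5A". This is an option, not a requirement.

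In Part A, Table 3 marks a predose test on Day 1, and its footnote c says tests "should be performed on all females of child-bearing potential at Screening, Day 1, and Follow-up".

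**The concern.** A pregnancy that begins after the Visit 5A or Visit 0B test would breach I4, but no scheduled test would show it before the first Part B dose. The next scheduled test is at Week 24. Clinic visits at Weeks 2, 6, 12 and 18 might reveal the pregnancy, but none includes a test. Section 10.2.2 states that nothing is known about effects on fetal development in humans.

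The blank cell looks like an oversight. The other tests and clinical assessments that Table 4 marks at Visit 5A are all marked again at Visit 1B: ECG, NYHA class, KCCQ-23, troponins, NT-proBNP, chemistry and hematology, and non-genetic biomarkers. Only the pregnancy test is not, and no reason is given.

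**Working it through.** The protocol gives no figure for the age of the pregnancy result, so there is none to reproduce. The question is how old the last scheduled result can be at the first Part B dose.

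**Inputs**

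- Longest gap from Part A completion to Part B start without rescreening: 56 days (Table 4, footnote l).
- Visit 5A: 14 to 21 days after the last Part A dose, which is taken on the day of Visit 4A (Section 6.1.1).
- Visit 0B window: Day -28 to Day -1 (Table 4).
- Next scheduled test after Visit 1B: Week 24, or 24 × 7 = 168 days.
- Part A completion is not defined as Visit 4A or Visit 5A, so both readings are worked.

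**Age of the last scheduled result at the first Part B dose**

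- Visits 5A and 1B combined: 0 days.
- Not rescreened, separate days, completion = Visit 5A: up to 56 days.
- Not rescreened, separate days, completion = Visit 4A: up to 56 − 14 = 42 days if Visit 5A is on day 14, or 56 − 21 = 35 days if it is on day 21.
- Rescreened: up to 28 days.

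**Longest interval between scheduled tests, not rescreened (nominal visit days)**

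- Completion = Visit 5A: 56 + 168 = 224 days.
- Completion = Visit 4A: 42 + 168 = 210 days.

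**Contraception cover**

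Part A criterion I6 requires contraception "from the Screening visit through 3 months after the last dose of study drug". The latest unrescreened Visit 1B falls 21 + 56 = 77 days after the last Part A dose, inside 3 months (about 91 days). The requirement therefore runs through the whole unrescreened gap.

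It need not do so before rescreening. The hiatus between the two parts has no stated limit, the Part A requirement ends 3 months after the last dose, and the Part B requirement starts at Part B consent.

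**Expected number of pregnancies**

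Section 10.2.3 defines highly effective contraception by a failure rate below 1% per year when used consistently and correctly. Over 56 days this is at most 1% × 56/365 = 0.15% per woman. Suppose, as an extreme, that all 40 planned Part A completers were women of childbearing potential at the maximum gap. Then the expected number is at most 40 × 0.0015 = 0.06.

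**With a predose test at Visit 1B**

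The age of the result is 0 days in every case. The longest interval to the next scheduled test falls from 224 (or 210) days to 168.

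**The case against.** The strongest reply is that the eligibility rules already cover this. The lead-in to the Part B exclusions applies them from Part A completion to Part B, Note 1 requires evaluation before dosing, and I4 separately bars pregnant women. Section 10.2.1 adds that women of childbearing potential should be tested. If completion means Visit 5A, it is even arguable whether a Visit 5A result covers the period after completion. A site therefore has a duty to establish pregnancy status and may test at Visit 1B. This stands as far as it goes, but none of these passages schedules a test, fixes its timing or limits the age of a result.

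The risk is also small. With correct contraception the extreme case above gives about 0.06 pregnancies. The true figure under correct use should be lower, because both sexes enrol, ages run to 80, Part B is optional and visits may be combined; imperfect use would raise it. This limits the weight of the point. It does not make contraception a substitute for a test: Part A requires contraception from Screening and still tests before the first dose.

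Two further points are fair. Tests follow at Weeks 24, 48, 72 and 96 and at early termination, so one result does not cover the whole of Part B. The remedy also leaves the 24-week interval after Visit 1B as it is.

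**Conclusion.** The concern holds. Under the schedule as written, a woman who is not rescreened and does not combine Visits 5A and 1B can begin Part B on a pregnancy result up to 56 days old, or 42 days if Part A completion means Visit 4A. A rescreened woman's result can be up to 28 days old. These figures follow from the schedule and need no assumption beyond the meaning of completion, where both readings are given.

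It is a weakness in test recency, not a conflict within the protocol, because a negative Visit 5A result can formally satisfy E7. The number of women affected cannot be stated: Part A plans about 40 completers of both sexes, and Part B has no target size. The case rests on individual safety and on consistency with Part A's own predose test, not on a large expected number of events.

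**What to change.** In Table 4, mark a predose pregnancy test at Visit 1B for women of childbearing potential, matching the Day 1 test in Table 3. State that one test serves when Visits 5A and 1B are combined.

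The same mark covers women admitted to Part B without completing Part A, which Section 6.1.2 allows with Sponsor approval. Table 3 has no pregnancy test at the Part A early termination visit. If neither Visit 5A nor Visit 0B were held, their last scheduled test would be the one before the first Part A dose. The protocol does not say that non-completers skip Visit 5A, so this is a conditional case.

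The cost is one added mark in the table and one routine urine or blood test for the women concerned, at a visit where blood is already drawn.

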APPENDIX 2 LABORATORY ASSESSMENTS

Hematology ^a	Serum Chemistry ^a
• CBC, including differential count	• Sodium
• Platelet count	Potassium
	Chloride
	Bicarbonate
	Total protein
	Albumin
	• Calcium
	Magnesium
	• Creatinine
	• ALP
	• ALT
	• AST
	Total bilirubin
	• Glucose
	• CK
	• BUN or urea (per local standards)
	• LDH
	Inorganic phosphorus
	Total cholesterol
	• eGFR
	• Uric acid
	• Amylase
	• Lipase

Table 6: Safety Laboratory Parameters

ALP = alkaline phosphatase; ALT = alanine aminotransferase; AST = aspartate aminotransferase; BUN = blood urea nitrogen; CBC = complete blood cell count; CK = creatine kinase; eGRF = estimated glomerular filtration rate; LDH = lactic acid dehydrogenase

^a All samples will be assayed in the central laboratory at all timepoints except when deemed necessary by Investigator's judgement

Troponins and NT-proBNP will also be assessed (APPENDIX 1).

The following nonsafety laboratory parameters will be measured in this study:

- FSH
- Pregnancy, assessed in urine or blood, based on the policy of the local institution or regulating Health Authority (eg, requirement for serum-based testing in the United Kingdom and Germany)
- TSH, Fe/TIBC/ferritin for Screening

